8.2 Study Drug Exposure Variables

Study Treatment Duration

Study treatment duration (days) is defined as (the last dose date – the first dose date +1) for mectinostat and as (the last dose date – the first dose date +29) for durvalumab.

Days on Study Drug

Days on study drug is defined as the total number of days patient received drug, after subtracting time for interruptions or drug missed, that is, the latest Stop Date - the earliest Start Date captured on the Study Drug Administration CRF page – number of days with 0 mg dose +1 for mectinostat and the latest Stop Date - the earliest Start Date captured on the Study Drug Administration CRF page – number of days with 0 mg dose +29 for durvalumab.

Cumulative Dose Received

For durvalumab, cumulative dose received (mg) is defined as the total amount of durvalumab a patient receives during the study, that is, the sum of dose administered as recorded on the Durvalumab Administration CRF form where dose administered equals 1500 when the planned dose was administered and is equal to the result of “If No, Dose Other Specify” question if the planned dose was not administered.

For mectinostat, cumulative dose received (mg) is defined as the total amount of mectinostat a patient receives during the study, that is, Sum of [(Stop date – Start date + 1) * Dose administered * Number of doses during this period of time] as recorded on the Mectinostat Administration CRF form.

Cycles Started

A patient is considered to have started a cycle if they received at least one dose in that cycle, per the Study Drug Administration CRF page.

Dose Intensity

Absolute Dose intensity (mg/day) is calculated as cumulative dose received (mg) / Treatment duration (days).

Relative dose intensity is calculated as the cumulative dose received (mg) / initial planned cumulative dose (mg). Initial planned cumulative dose is calculated as the starting dose (day 1 cycle 1) multiplied by the study treatment duration.

Sponsor: Mirati Therapeutics, Inc.
Protocol no: 0103-020

Compliance is calculated as cumulative dose received (mg) / cumulative planned dose (mg, including dose decreased and interruptions as per physician's decision).

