### 3 STUDY DESIGN

Study 0103-020 is an open-label Phase 1/2 evaluation of mocetinostat in combination with durvalumab. The Phase 1 segment will define the RP2D of mocetinostat to be used in combination with the full dose regimen of durvalumab; eligible patients will have an advanced solid tumor disease that is not amendable to curative treatment. The Phase 2 segment will evaluate the clinical activity of mocetinostat in combination with durvalumab, as assessed by ORR in accordance with RECIST 1.1., in patients with locally advanced, unresectable or metastatic NSCLC who have previously received at least one platinum-containing doublet chemotherapy regimen for advanced disease. Patients who have previously received treatment with checkpoint inhibitors may be enrolled in the Phase 1 assessment and will be enrolled into dedicated cohorts in the Phase 2 assessment. Secondary objectives include secondary efficacy endpoints, PK, incidence of ADA and change in tumor PD-L1 expression.

The Schedule of Assessments to be performed in the study is presented in [Table 1](#). Triplicate ECG assessments, PK, and ADA collection time points are presented in [Table 2](#).

The treatment regimen to be evaluated in this study includes a 7-Day Lead-in Period of mocetinostat single agent administered TIW (e.g., Monday, Wednesday and Friday) followed by administration of the combination regimen with durvalumab. The RP2D dose of mocetinostat will be established in successive dose escalation cohorts in the Phase 1 study and utilized in the Phase 2 study. The dose and regimen of durvalumab to be used throughout the study is 1500 mg on Day 1 of each 28-day cycle (i.e., Q4W). Guidelines for adverse event management and associated treatment modifications of each agent are provided in [Section 5](#).

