### **3.1.4 Definition of Recommended Phase 2 Dose**

The RP2D will be the highest dose of mocetinostat evaluated that is associated with:

- sufficient safety/tolerability to anticipate that patients will typically be able to receive treatment with at least 75% of the intended dose intensity of mocetinostat and 100% dose intensity of durvalumab; and
- no observed  $\geq$ Grade 3 or serious irAEs causally related to the combination regimen.

A dose level below the MTD may be selected as the RP2D.

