6.0 Study Design

This is an open-label Phase 1/2 evaluation of mocetinostat in combination with durvalumab. The Phase 1 segment will define the RP2D of mocetinostat to be used in combination with full dose regimen of durvalumab; eligible patients will have an advanced solid tumor disease that is not amendable to curative treatment. The Phase 2 segment will evaluate the clinical activity of mocetinostat in combination with durvalumab, as assessed by ORR in accordance with Response Evaluation Criteria in Solid Tumors (RECIST) version 1.1, in patients with locally advanced, unresectable or metastatic NSCLC who have previously received at least one platinum-containing doublet chemotherapy regimen for advanced disease. Patients who have previously received treatment with checkpoint inhibitors may be enrolled in the Phase 1 assessment and will be enrolled into dedicated cohorts in the Phase 2 assessment. Secondary objectives include secondary efficacy endpoints, PK, incidences of ADA and change in tumor PD-L1 expression.

The schedule of assessments to be performed in the study is presented in [Table 1](#). Triplicate electrocardiogram (ECG) assessments, PK, and ADA collection time points are presented in [Table 2](#).

The treatment regimen to be evaluated in this study includes a 7-Day Lead-In Period of mocetinostat single agent administered three times weekly (TIW; e.g., Monday, Wednesday and Friday) followed by administration of the combination regimen with durvalumab. The RP2D dose of mocetinostat will be established in successive dose escalation cohorts in the Phase 1 portion of the study and utilized in the Phase 2 portion of the study. The dose and regimen of durvalumab to be used throughout the study is 1500 mg on Day 1 of each 28-day cycle (i.e., Q4W).

Sponsor: Mirati Therapeutics, Inc.

Protocol no: 0103-020

Table 1: Schedule of Assessments

The Schedule of Assessments provides an overview of the protocol visits and procedures. Refer to Section **Error! Reference source not found.** for detailed information on each assessment. Additional, unplanned assessments should be performed as clinically indicated, including for the purpose of fully evaluating adverse events.

Assessments	Screen/ Baseline	7-Day Mocetinostat Lead-In Period	Mocetinostat + Durvalumab				End of Treatment ¹⁵		
			Cycle 1		Cycle 2 and 3				

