Lead-In Day 1	Pre- ⁴ and post-dose (1 hour only)	Phase 1: Pre- and post-dose (1, 3 and 7 hour) Phase 2: Pre- and post-dose (1 hour)		
Cycle 1 Day 1 (Day 1, Week 1)	Pre- and post-dose (1 hour only)	Phase 1: Pre- and post-dose (1, 3 and 7 hour) Phase 2: Pre- and post-dose (1 hour)	Pre-dose and end-of-infusion	Pre-dose
Cycle 1 Day 15 (Day 15, Week 3)		Pre- and post-dose (1 hour)	Pre-mocetinostat dose	
Cycle 2 Day 1 (Day 29, Week 5)	Pre- and post-dose (1 hour)	Pre- and post-dose (1 hour)	Pre-dose	Pre-dose
Cycle 3 Day 1 (Day 57, Week 8)		Pre- and post-dose (1 hour)	Pre-dose	
Cycle 4 Day 1 (Day 85, Week 13)			Pre-dose and end-of-infusion	Pre-dose
Cycle 7 Day 1 (Day 169, Week 25)		Pre-dose	Pre-dose	Pre-dose
Long Term Follow-up			90-days after last dose	90-days after last dose

1. On days mocetinostat and durvalumab are both administered and scheduled for PK assessment, mocetinostat dosing and sampling should precede durvalumab dosing.
2. The typical durvalumab infusion duration is 1-hour. End-of-infusion samples are to be collected within 5 minutes from the contralateral arm.
3. ECGs should be taken in triplicate, with readings at least 2 minutes apart. QTc should be manually calculated using Fridericia's formula.
4. On Lead-In Day 1, two sets of triplicate ECGs should be done within 1 hour prior to dosing (e.g., at 20-30 minute intervals) to firmly establish the baseline. In general, ECGs should be performed prior (within -30 to -5 minutes) to the respective PK blood collection.
5. Scheduled vital signs and triplicate ECGs precede PK sample collection in all cases.
6. Pre-dose sample allowable window up to 30 minutes prior to dose in all cases.
7. Allowable windows for mocetinostat post-dose samples are plus or minus 30 minutes for 1 hour post-dose and plus or minus 1 hour for 3 and 7 hour samples.

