12.3 Treatments

12.3.1 Extent of Study Treatment Exposure

Exposure to treatment will be summarized by dose level for the Safety population separately for mocetinostat and durvalumab. Descriptive statistics will be provided for the duration of exposure (weeks), the total number of cycles started, number of doses received, cumulative dose received (mg) and dose intensity (mg/week).

Number and percentage of patients with at least 1 dose reduced (only for mocetinostat), at least 1 dose interrupted and reasons for dose reduction and interruption will be presented separately for mocetinostat and durvalumab.

Information regarding patients' dosing regimens will be listed separately for mocetinostat and durvalumab.

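### SAP 8.2 makes durvalumab treatment duration one day too long per patient, and its Days on Study Drug formula does not remove the time lost to a skipped infusion

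*SAP*

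**What the plan says.** The regimen is "1500 mg on Day 1 of each 28-day cycle" (Protocol 3; SAP 6.0 says the same). The sampling schedule in SAP Table 2 has a row labelled "Cycle 2 Day 1 (Day 29, Week 5", so one infusion covers Days 1 to 28.

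SAP 8.2 defines two durvalumab time variables:

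- Study Treatment Duration is the last dose date minus "the first dose date +29) for durvalumab". The corresponding mocetinostat formula adds 1.
- Days on Study Drug is described as time on drug net of interruptions and missed doses. Its formula takes the latest stop date minus the earliest start date and then subtracts the "number of days with 0 mg dose +29 for durvalumab".

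Absolute dose intensity is cumulative dose divided by treatment duration in days. SAP 12.3.1 tabulates dose intensity in mg/week together with "duration of exposure (weeks", and does not say which of the two variables the latter uses.

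**The concern.** With a 28-day cycle, the constant that turns last-minus-first dose date into days covered is 28. Adding 29 runs the duration into Day 1 of a cycle for which no infusion was given. Since duration is the denominator of dose intensity, a patient treated exactly to plan appears slightly under-dosed.

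The second formula does not do what its own description says. For a drug given once every 28 days, the number of dates carrying a 0 mg dose is not the time without drug. A patient who skips an infusion can therefore be credited with most or all of the skipped cycle.

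What is at stake is the accuracy of the exposure table. No hypothesis test, primary endpoint or stopping rule uses these variables.

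**Working it through.** **Inputs.** Dose 1500 mg and cycle length 28 days (Protocol 3, SAP 6.0); Cycle 2 Day 1 on Day 29 (SAP Table 2); window of ±2 days on Day 1 visits from Cycle 2 (Table 1); the formulas of SAP 8.2. The nominal rate is 1500 / 4 weeks = 375 mg/week, or 1500 / 28 = 53.57 mg/day. The SAP does not state this benchmark; it follows from the regimen.

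**Where 29 could come from.** For n on-schedule infusions, last minus first dose date is 28(n − 1). Days covered are 28n, which requires +28. The value +29 results only from counting inclusively up to the day 28 days after the last infusion. For one infusion that is Day 29, which is Day 1 of the next cycle. The mocetinostat +1 counts the last dosing day; for durvalumab that day is already among the 28.

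**Treatment duration and dose intensity, on schedule.** Duration is 28(n − 1) + 29 = 28n + 1. Dose intensity is 1500n × 7 / (28n + 1) mg/week, and its ratio to nominal is 28n / (28n + 1).

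| Infusions | SAP days | Days covered | mg/week | % of 375 |
|---|---|---|---|---|
| 1 | 29 | 28 | 362.1 | 96.6 |
| 2 | 57 | 56 | 368.4 | 98.2 |
| 6 | 169 | 168 | 372.8 | 99.4 |
| 12 | 337 | 336 | 373.9 | 99.7 |

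With +28, every row gives 28n days and 375 mg/week.

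**Effect of the visit window.** If the last infusion is one day early, duration is 28(n − 1) − 1 + 29 = 28n, exactly 100% for any n ≥ 2. Two days early gives 56/55 = 101.8% at n = 2 and 168/167 = 100.6% at n = 6. With one infusion there is no interval to vary, so 96.6% stands.

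**Days on Study Drug with a skip.** Take infusions in Cycles 1 and 3, with Cycle 2 skipped. Last minus first is 56 days, and the two infusions cover 2 × 28 = 56 days. The SAP does not say how a skip is recorded, so three conventions are shown:

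- Skip not recorded as 0 mg: 56 − 0 + 29 = 85 days.
- Skip recorded as one 0 mg date: 56 − 1 + 29 = 84 days (84/56, or 50% too many).
- Skip recorded as 28 zero-dose days: 56 − 28 + 29 = 57 days.

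None of the three returns 56. With six scheduled infusions and one skipped mid-course, one 0 mg date gives 140 − 1 + 29 = 168 days and 28 zero-dose days give 140 − 28 + 29 = 141, against 5 × 28 = 140 covered.

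**Relative dose intensity.** SAP 8.2 takes the planned dose as the starting dose multiplied by duration in days. Read literally, an on-schedule durvalumab patient has 1500n / (1500 × (28n + 1)): 1/29 = 3.45% at one infusion and 12/337 = 3.56% at twelve. With +28 it is 1/28 = 3.57% throughout. A per-infusion dose is being multiplied by days. This is a separate error, and the change of constant leaves it in place.

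**The case against.** The other side's main arguments are these.

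- **The size is small.** One day per patient is 0.14 week, and the relative error falls from 3.6% of duration at one infusion to 0.3% at twelve. This stands. A reader might take the formula to credit 29 days to every infusion; it does not, because the constant is added once, after the last dose.
- **100% is attainable.** One might infer that no patient can reach full durvalumab dose intensity. That holds only for patients with one infusion, or with infusions exactly on schedule or late. The ±2-day window allows 100% or more from two infusions on. Compliance as defined in SAP 8.2 does not use duration at all.
- **The RP2D is not affected.** Protocol 3.1.4 refers to "100% dose intensity of durvalumab", and it is tempting to conclude that the formula biases the choice of dose. The criterion is a forward-looking judgement about what patients will typically be able to receive. Neither document links it to SAP 8.2 or to the exposure table.
- **The CRF convention is unknown.** The 84-day figure assumes that a skip appears as one 0 mg date. The SAP describes the durvalumab form as a record per administration, which makes this the natural reading, but it remains an assumption. What does not depend on it is that none of the three conventions gives the days covered.
- **Reach.** Days on Study Drug does not enter dose intensity. It affects the exposure table only if it is the source of the exposure duration, which SAP 12.3.1 leaves open.

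**Conclusion.** Both formulas are wrong as written, and the consequences are limited to descriptive output.

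Treatment duration is one day too long per patient, given a 28-day cycle. Dose intensity for on-schedule patients is therefore understated by 3.4% of nominal at one infusion, 1.8% at two and 0.6% at six. This understatement is certain with a single infusion; with more, timing within the visit window can cancel or reverse it.

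Days on Study Drug does not deliver its stated intent. In the three-cycle example it is too high by 1 to 29 days on 56, depending on an unstated recording convention. This is the more consequential of the two if that variable feeds the exposure table.

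The documents support no conclusion about RP2D selection. The correction is worth making because it is cheap, not because a trial decision turns on it.

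**What to change.** In SAP 8.2:

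- Use +28 in both durvalumab formulas, with dates taken from the first and last administered (non-zero) infusions.
- In Days on Study Drug, replace the count of 0 mg days by 28 days for each infusion omitted between those two doses. The restriction matters: with infusions in Cycles 1 and 2 and Cycle 3 omitted, an unrestricted deduction gives 28 − 28 + 28 = 28 days against 56 covered.

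In SAP 12.3.1, name the duration variable that is tabulated.

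In the same edit, but as a separate correction, put the planned dose in relative dose intensity on the dosing-interval scale, and align the mg/day of SAP 8.2 with the mg/week of SAP 12.3.1.

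The cost is a few lines in the SAP and the derived-dataset specification, with no new data. SAP 4.0 already foresees a final version before database lock.

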6.1.2 Dose Escalation Plan

The first cohort of patients to be enrolled will begin with the mocetinostat 7-Day Lead-In Period, receiving 50 mg on 3 days (e.g., Monday, Wednesday and Friday) and will continue into the combination regimen, with 50 mg mocetinostat administered TIW and 1500 mg durvalumab administered Q4W.

For a patient within a dose cohort to be considered evaluable for the dose-escalation decision, the patient must have either been on study for 1 full cycle and have received treatment with durvalumab and at least 9 of 12 scheduled mocetinostat doses (75%) in Cycle 1 or have experienced a DLT in Cycle 1.

Decision making rules for cohort expansion and dose escalation or de-escalation based on the experience of patients treat at a dose level are presented in [Appendix 3](#).

To ensure sufficient patient experience at the dose selected as the RP2D, enrollment at any dose level under consideration may be expanded to include at least 6 patients.

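### SAP 8.2 omits dosing frequency from the planned cumulative dose, so a fully compliant patient shows a relative dose intensity of 3.4–3.6% for durvalumab and about 43–46% for mocetinostat after four weeks or more (descriptive variable; minor)

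*SAP*

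**What the plan says.** SAP 8.2 (Study Drug Exposure Variables) gives treatment duration in days: last minus first dose date plus 1 for mocetinostat, and last dose date minus "the first dose date +29) for durvalumab". The same +29 appears again under Days on Study Drug.

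The ratio at issue is defined in two sentences: "Relative dose intensity is calculated as the cumulative dose received (mg) / initial planned cumulative dose (mg"), followed by "Initial planned cumulative dose is calculated as the starting dose (day 1 cycle 1) multiplied by the study treatment duration". No dosing-frequency term appears in either.

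The schedules are in SAP 6.0: a "7-Day Lead-In Period of mocetinostat single agent administered three times weekly", continued at that frequency in the combination, and durvalumab "1500 mg on Day 1 of each 28-day cycle (i.e., Q4W"). SAP 6.1.2 counts the doses itself when it requires "at least 9 of 12 scheduled mocetinostat doses (75%) in Cycle 1".

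For durvalumab, cumulative dose received is the sum of the doses given, which is correct. For mocetinostat, 8.2 says in words that it is the total amount received. It then gives a formula that multiplies the days in each record by "Dose administered * Number of doses during this period of time".

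SAP 8.2 states absolute dose intensity in mg/day, whereas SAP 12.3.1 lists "cumulative dose received (mg) and dose intensity (mg/week") among the statistics to be reported.

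**The concern.** Milligrams per administration multiplied by calendar days gives the planned total of a once-daily drug. For these schedules that is more than twice the mocetinostat plan and about 28 times the durvalumab plan. A patient who misses nothing would appear to have received under half of one drug and almost none of the other.

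Protocol 9.5.5 commits to describing treatment in terms of dose intensity, and SAP 8.2 is where the term is defined. SAP 4.0 says that SAP1 is finalized so that programming can begin, with SAP2 to follow before database lock. Unless the definition is corrected, the formula may be coded as it stands.

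**Working it through.** The documents state no value of relative dose intensity, so there is none to reproduce. The check applies the 8.2 definitions to a patient who takes every scheduled dose. The milligram dose cancels, so the results hold at every dose level.

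**Inputs.** Three mocetinostat doses per 7 days, Monday/Wednesday/Friday, lead-in included (SAP 6.0); 12 per 28-day cycle (SAP 6.1.2); one durvalumab dose per 28 days (SAP 6.0); durations +1 and +29 days (SAP 8.2). The numerator is the true total dose received.

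**Mocetinostat.** After k full weeks with the last dose on a Friday, doses = 3k and days = 7k − 2, so the ratio is 3k/(7k − 2).

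| Full weeks | Doses/days | Ratio |
|---|---|---|
| 1 | 3/5 | 60.0% |
| 2 | 6/12 | 50.0% |
| 3 | 9/19 | 47.4% |
| 4 | 12/26 | 46.2% |
| 5 (lead-in + Cycle 1) | 15/33 | 45.5% |
| 25 (lead-in + 6 cycles) | 75/173 | 43.4% |
| limit | 3/7 | 42.9% |

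Stopping on the Monday or Wednesday of week 5 gives 13/29 = 44.8% or 14/31 = 45.2%. A patient with all 3 lead-in doses and 9 of the 12 Cycle 1 doses, the last on the Friday of week 5, has received 12/15 = 80% of plan but shows 12/33 = 36.4%.

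**Durvalumab.** With n doses at exact 28-day intervals, days = 28(n − 1) + 29 = 28n + 1, so the ratio is n/(28n + 1). One dose gives 1/29 = 3.4% and six give 6/169 = 3.6%; the limit is 1/28 = 3.6%.

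**Would duration in weeks repair it?** No. Durvalumab becomes 1/(29/7) = 24.1% after one dose and 6/(169/7) = 24.9% after six. Mocetinostat becomes 12/(26/7) = 323% at four weeks, with limit 300%.

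**The +29.** One dose gives 1500 × 7/29 = 362 mg/week and six give 9000 × 7/169 = 373 mg/week, against a planned 1500/4 = 375. That is 3.4% and 0.6% low.

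**Mocetinostat cumulative dose.** If the dose-count field is the total for the record, the formula divided by the true amount is (days × dose × doses)/(dose × doses) = days in the record. The factor is 1 for one-day records. As illustrations only, it is 5 for an assumed Monday–Friday record and 26 for an assumed record from the Monday of week 1 to the Friday of week 4. In the last case the ratio in the table would read 12 × 26/26 = 1200% instead of 46.2%.

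**Testing the replacement denominators.**
- Mocetinostat as a rate, starting dose × 3/7 × days, gives 12/(3 × 26/7) = 107.7% at four weeks. Counting scheduled doses gives 13/13, 14/14 and 15/15 = 100% for the three week-5 stopping days.
- Durvalumab as a count of doses scheduled between first and last dose hides delay: doses on Days 1 and 43 cover scheduled Days 1 and 29, giving 2/2 = 100%. As (last − first + 28)/28, the same patient has (42 + 28)/28 = 2.5 planned doses and 2/2.5 = 80%. At exact 28-day intervals, (28(n − 1) + 28)/28 = n, giving 100%.

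**The case against.** The strongest reply is that little depends on this variable. SAP 12.3.1 names absolute dose intensity and does not name relative dose intensity. The table shells are a separate document, so the plan does not show that the ratio will be tabulated. Absolute dose intensity and the compliance ratio do not use the faulty denominator, and the SAP is expressly to be reissued before lock. All of this stands and sets the severity at minor. It does not make the definition right.

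The mocetinostat figure is also conditional. It takes the numerator as 8.2 words it, the total received, and it needs about four weeks of treatment. Both conditions belong with the number. The durvalumab figure needs neither.

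A reader might infer that a compliant patient would fail the RP2D criterion, which speaks of 75% mocetinostat and 100% durvalumab dose intensity. The documents do not support that. SAP 6.1.4 is a forward-looking judgement about what patients will typically tolerate, and it does not refer to 8.2. DLT evaluability uses a count of doses, and the ORR analysis uses no exposure variable.

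A reader might also infer that mocetinostat cumulative dose is certainly overstated. That depends on the CRF layout, which the documents do not show. If records cover one day the multiplier is harmless, and if the dose-count field holds a rate, removing the multiplier would understate the dose.

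Finally, +29 can be read as an inclusive day plus a 28-day interval. That is a possible convention, but it credits one 28-day cycle with 29 days.

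**Conclusion.** The defect holds: SAP 8.2 carries no frequency term, no other section supplies one, and reading duration in weeks rescues neither drug. With the true dose received as numerator, full compliance shows as 3.4–3.6% for durvalumab at any duration. For mocetinostat it shows as about 43–46% after about four weeks or more, and 47–60% at the end of the first three full weeks. These figures assume Monday/Wednesday/Friday dosing and exact 28-day intervals.

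Severity is minor. Relative dose intensity is descriptive, is not named in 12.3.1, and is not cited by the ORR, DLT or RP2D rules. The +29 does enter durvalumab quantities that 12.3.1 reports, but its effect is small. The mocetinostat day multiplier is a query; if records span several days, it would affect the reported cumulative dose and dose intensity, and the compliance ratio, which has the same numerator.

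**What to change.** Reword SAP 8.2 in SAP2:

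- **Mocetinostat planned cumulative dose:** starting dose × number of doses scheduled at three per week, on a calendar fixed at the first dose date (lead-in included), through the last dose date. Held or missed doses stay in the count.
- **Durvalumab planned cumulative dose:** 1500 mg × (last dose date − first dose date + 28)/28. Full compliance gives 100% and delayed cycles lower the ratio. A dose shifted within the ±2-day visit window moves it slightly: a second dose on Day 31 gives 2/(58/28) = 96.6%.
- **+29 to +28** in both Study Treatment Duration and Days on Study Drug. Changing only the first would give 29 days on drug within a 28-day duration after a single dose.
- **Mocetinostat cumulative dose:** check the CRF page. If the dose-count field is the total for the record, remove the (stop − start + 1) multiplier. If it is a rate, state the unit and write the formula accordingly.
- **Dose intensity:** use mg/week in both 8.2 and 12.3.1.

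The mocetinostat duration (+1) can stay. The cost is a rewording and the matching program changes before final programming, with no new data.
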